7.4 Effect Modification Analyses of the Primary Outcome

We will examine whether pre-specified baseline variables modified the effect of treatment group on the primary outcome using tests of statistical interaction in a proportional odds regression model. Independent variables will include study group assignment, the potential effect modifier of interest, the interaction between the two, and the same pre-specified covariates used in the primary model. Presence of effect modification will be assessed by reference to the P value for the interaction term, with values less than 0.10 considered to suggest a potential interaction and values less than 0.05 considered to confirm an interaction.

We will examine whether the following pre-specified baseline variables modify the effect of study group on the primary outcome:

1. Clinical status at randomization as assessed by the four categories of the seven-category ordinal outcome scale for which patients could qualify at randomization:
 - a. Receiving ECMO, invasive mechanical ventilation, or both
 - b. Receiving noninvasive mechanical ventilation, nasal high-flow oxygen therapy, or both

- c. Receiving supplemental oxygen
- d. Not receiving supplemental oxygen
2. Located in an intensive care unit at randomization (Yes, No)
3. Sequential Organ Failure Assessment (SOFA) score at randomization
4. Duration of symptoms of acute respiratory infection prior to randomization
5. Age
6. Sex
7. Race and ethnicity

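### SAP 7.4 counts an unadjusted interaction P<0.05 as confirmation for each of seven modifiers: with no true effect modification, the chance of at least one false confirmation is about 30% if the tests are independent and roughly 25-30% under plausible correlation

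*SAP*

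**What the plan says.** SAP section 7.4 introduces a numbered list of modifiers with "We will examine whether the following pre-specified baseline variables modify the effect of study group on the primary outcome". The list has seven items: clinical status at randomization, ICU location (yes or no), SOFA score, symptom duration, age, sex, and race and ethnicity. The first is given in four categories ("Clinical status at randomization as assessed by the four categories of the seven-category ordinal outcome scale for which patients could qualify at randomization"). The last is entered as the single item "Race and ethnicity", and its coding is not stated.

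Each modifier gets its own proportional odds model: "Independent variables will include study group assignment, the potential effect modifier of interest, the interaction between the two", plus the covariates of the primary model. The P value for the interaction is then read by a two-tier rule: "values less than 0.10 considered to suggest a potential interaction and values less than 0.05 considered to confirm an interaction".

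Neither document adjusts these tests for multiplicity, states a family-wise error rate for them, or calls them exploratory. Protocol section 7.1 is more modest. It says only that data will also be reported separately by ICU location and by symptom duration (up to 5 days versus longer), and it sets no significance threshold.

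**The concern.** The upper tier of the rule is a written decision criterion. A single nominal P<0.05, found anywhere among seven tests, is to be described as confirming that the effect of hydroxychloroquine differs between kinds of patient. A reader will attach a 5% false-positive risk to that word. The risk across the set is several times larger, because the rule gives seven chances to cross the line.

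What is at stake is the wording of the subgroup conclusions. A trial with no real effect modification could, by following its own plan, report a confirmed differential effect by age, sex, race, severity or symptom duration, and that statement could be taken up as a reason to treat or withhold treatment in a subgroup.

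**Working it through.** The documents give no family-wise figure for these tests, so there is none to reproduce.

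**Inputs from SAP 7.4**
- Threshold for confirmation: 0.05 per test.
- Number of tests: 7, taking one interaction test per listed modifier.
- Scenario: no true effect modification for any of the seven.

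**Independent tests**
- P(at least one P<0.05) = 1 - (1 - 0.05)^7 = 1 - 0.6983 = 0.302.
- Expected number of false confirmations = 7 × 0.05 = 0.35.

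**Correlated tests**

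Independence will not hold exactly. Protocol 7.1 describes patients randomized in the ICU as tending to be sicker. SAP Appendix B builds the respiratory part of SOFA from oxygenation and inspired oxygen, which overlaps with the oxygen-support categories of clinical status. The documents give no correlations, so a range was assumed. Seven two-sided z-tests were simulated as multivariate normal, with correlation r among the tests for clinical status, ICU location and SOFA and independence elsewhere (1,000,000 draws per r).

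| Assumed r among the three severity tests | P(at least one P<0.05) |
|---|---|
| 0.3 | 29.6% |
| 0.5 | 28.8% |
| 0.7 | 27.5% |
| 0.8 | 26.6% |
| 0.9 | 25.4% |

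If those three tests were completely redundant, five independent tests would remain: 1 - 0.95^5 = 22.6%. With one common correlation across all seven tests (500,000 draws per r), the figures are 28.9%, 27.1% and 23.0% at r = 0.2, 0.3 and 0.5.

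**Number of tests**

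If race and ethnicity were tested separately there would be eight tests, and the independent figure becomes 1 - 0.95^8 = 33.7%. If clinical status is categorical it has three interaction terms; reading a P value for each would also take the count above seven. The SAP does not say whether a joint test is used.

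**How informative one nominal P<0.05 would be**

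Protocol 7.1 gives operating characteristics for an overall odds ratio of 1.8, not for interactions. Assume the outcome distribution in its Table 1 (11.5%, 5.8%, 21.9%, 60.8%), 510 patients and no covariate adjustment.
- Sum of cubed proportions = 0.0015 + 0.0002 + 0.0105 + 0.2248 = 0.237.
- Information for the log odds ratio = (510/12) × (1 - 0.237) = 32.4, so SE = 1/√32.4 = 0.176.
- Binary modifier split 50:50: interaction SE = 2 × 0.176 = 0.351. For a ratio of odds ratios of 1.8, z = ln(1.8)/0.351 = 0.588/0.351 = 1.67, and power at P<0.05 is about 39%.
- Split 20:80: interaction SE = 0.176 × √(1/0.2 + 1/0.8) = 0.439, z = 1.34, and power is about 27%.

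A rule that misses most large interactions, and has roughly a one-in-four to one-in-three chance of producing a false one somewhere in the set, cannot confirm anything on a single nominal P value.

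**The case against.** The strongest reply is that this concerns one verb in a supporting analysis. The modifiers are pre-specified baseline variables, each is tested by a formal interaction rather than by comparing within-subgroup P values, and all seven are listed, so a reader can discount accordingly. Many trials leave subgroup tests unadjusted. No decision in the documents turns on section 7.4.

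Much of that stands, and it limits the point. A reader might infer that the trial's main error rate is inflated. It is not: SAP 7.2 defines one primary analysis, and the stopping criteria in SAP 4.3 and protocol 7.1 use only the overall odds ratio. Pre-specification does guard against choosing modifiers after seeing the data. It does not control error across seven tests, and leaving subgroup tests unadjusted is defensible when they are presented as exploratory. Here the SAP claims confirmation instead.

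Three other stronger readings should be resisted.
- The 30% is not unconditional. It requires independent tests and no true effect modification anywhere.
- At the P<0.10 tier, 1 - 0.90^7 = 52% looks alarming, but the SAP says there only that an interaction may be present. That is already hedged, and a false hint is not a false claim.
- A reader might infer that the SAP tests every category separately. It speaks of the interaction in the singular, which is compatible with one test per modifier. The form of the test is unspecified, not shown to be wrong.

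**Conclusion.** The point holds as a should-fix on the strength of the conclusion. Under the rule as written, and if nothing modifies the treatment effect, the chance of at least one false confirmed interaction is 30.2% with seven independent tests and roughly 25-30% (25.4% to 29.6%) for assumed correlations of 0.9 down to 0.3 among the three severity modifiers. That is about five to six times the nominal 5%. The correlations are assumptions, and the count assumes one test per modifier; separate race and ethnicity tests or per-category tests would change it. An unadjusted P<0.05 on a pre-specified interaction remains some evidence, but weak evidence, and the word *confirm* is not justified.

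**What to change.** In SAP 7.4:
1. Delete the statement that P<0.05 confirms an interaction. State that all seven interaction tests are exploratory and unadjusted for multiplicity, so that P<0.05 is at most suggestive.
2. Report every interaction result with the number of tests done and with interval estimates of the effects, not only those below a threshold.
3. Specify one joint likelihood-ratio test per modifier for the multi-category variables, and state how race and ethnicity are coded.

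A Holm-adjusted threshold (first step 0.05/7 = 0.0071) is optional. It is needed only if the sponsor wants to keep a confirmatory claim, and it has a price: in the 50:50 example above, power at the first step falls from about 39% to about 15% (critical value 2.69 against z = 1.67). Reasonable statisticians would differ on whether that is worthwhile, including for interactions in the direction of harm.

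The cost is a few sentences, with no new data and no change to the primary analysis. The downside is that no interaction can be declared confirmed from this trial alone.

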7.5 Analysis of Secondary and Safety Outcomes

Ordinal secondary will be analyzed using a proportional odds model with randomized group assignment as an independent variable and the covariables used in the primary model. Binary secondary outcomes will be analyzed using multivariable logistic regression models with the same pre-specified covariates. Survival and hospital discharge through day 28 will be analyzed using multivariable proportional hazards regression with the same covariates in the primary outcome model. For the hospital discharge model, death will be treated as a competing risk, and the sub-distribution hazard ratio will be reported.⁶ Safety outcomes will be analyzed with simple logistic regression without co-variable adjustment.

Detailed data on receipt of invasive mechanical ventilation, vasopressors, intensive care unit admission, and hospitalization were collected during the index hospitalization, but not after discharge from the index hospitalization. Therefore, the main analysis of the associated “-free day” outcomes will use information regarding receipt of the supportive therapy between randomization and hospital discharge or Study Day 29, whichever occurs first (“in-hospital outcome”). Information on death between discharge from the index hospitalization and Study Day 29 is systematically available via follow-up phone calls. Hence, we will use all-cause, all-location death in the calculation of “-free day” outcomes.

7.6 Presentation of Adverse Events

The frequency and description of adverse events will be reported for all enrolled patients and by randomized group (hydroxychloroquine vs placebo).

7.7 Analysis of On-study Variables

Variables that are measured systematically at intermittent time points during the study will be presented at each time they are measured, stratified by randomized group. These analyses will include:

- QTc measurement on Study Day 2 (24-48-hour time window)
- COVID Ordinal Outcomes Scale on Study Days 2, 3, 4, and 5
- SOFA score on Day 3
- S/F ratio / Respiratory SOFA score on Day 3

7.8 Handling of Missing Data.

Primary Outcome. Primary outcome data will be complete for all patients hospitalized through Day 15 because all data needed to classify the primary outcome are available in the medical record. For patients discharge prior to Day 15, data for the primary outcome are collected via a telephone follow-up call. If primary outcome data are missing for patients who left the acute care PETAL hospital prior to Day 15, the following procedures will be used:

- Patients who left the hospital prior to Day 15 and did not have a COVID Ordinal Outcomes Scale collected via phone follow-up at Day 8 (either because they remained in the hospital from the index hospitalization on Day 8 or, if discharge prior to Day 8, were not reached by phone on Day 8), the primary outcome will be coded as a level 6 (not hospitalized with limitation in activity) on COVID Ordinal Outcomes Scale.
- Patients who completed a COVID Ordinal Outcomes Scale by phone follow-up on Day 8 will have the level from the Day 8 assessment carried forward to the Day 15 primary outcome assessment.

Covariates. We expect missing data for the pre-specified covariates in the proportional odds and logistic regression models to be rare. If missing data do exist for these covariates, values will be imputed using simple imputation of the median value from the trial population with non-missing data.

Secondary Outcomes. Data will not be imputed for secondary outcomes. The frequency of missing data will be reported.

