4.5 On-Study Monitoring

All patients enrolled in the study will be initially hospitalized and will therefore receive monitoring as a part of routine clinical care, including monitoring by their physicians, nurses, respiratory therapists, and ancillary staff.

In addition to routine clinical monitoring, enrolled patients will have an assessment of the QTc with an electrocardiogram (EKG) or rhythm strip performed 24-48 hours after administration of the first study medication. If an EKG or rhythm strip has been performed as a part of clinical care during this window, study personnel will assess the QTc on these clinically performed tracings. If an EKG or rhythm strip has not been performed as a part of clinical care during this window, an EKG or rhythm strip will be ordered and performed as a part of study procedures. This QTc will be used to monitor patient safety and inform stopping of the study drug as described below. If a patient is discharged from the hospital before the QTc is evaluated at 24-48 hours, the study drug may be continued after discharge without this assessment.

Between randomization and Day 5, study personnel will review the electronic health record daily for potential medication interactions with hydroxychloroquine (see Appendix B). If a medication that is considered to be contraindicated with hydroxychloroquine is discovered, treating clinicians will be contacted to discuss if stopping study drug is appropriate or if the medication in question can be stopped or substituted. If a medication with a potential interaction with hydroxychloroquine is identified, study

personnel will contact treating clinicians to ensure they are aware of the potential interaction. Treating clinicians will determine whether an alternative medication would be appropriate or whether the risk-benefit ratio favors continuing the medication with the known potential interaction. If a patient is started on a medication listed in Appendix B that potentially prolongs the QTc, study personnel will recommend to treating clinicians use of continuous cardiac monitoring when available during the study drug treatment period.

In addition to manual monitoring by study personnel for medication interactions, many electronic health records contain tools within the electronic order entry system to automatically screen for medication interactions with hydroxychloroquine and notify ordering providers of the potential interaction at the time of order entry.

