4.6 Criteria for Stopping Study Drug

Administration of the blinded study drug may be stopped temporarily or permanently for (a) adverse events, (b) results of on-study monitoring, (c) clinical deterioration, or (d) evidence of an alternative cause to the patient's symptoms.

If a patient experiences an adverse event that the patient (or legally authorized representative), treating clinicians, or investigators feel merits temporarily or permanently stopping the study drug, the study drug will be stopped. The explanation for stopping the study drug will be recorded in the case report form, and the adverse event will be recorded and reported according to the adverse event guidelines below. If the adverse event resolves to the extent that the patient (or legally authorized representative), treating clinicians, and investigators feel that resuming the study drug is appropriate, the study drug will be resumed, and this information will be recorded in the case report form.

If a QTc assessed after randomization is >500 ms, the study drug will be discontinued for 24 hours and a repeat EKG will be performed daily until either the QTc is less than 500 ms, at which time study drug is resumed until 5 days after randomization with daily QTc assessments, or until 5 days after randomization is reached without resumption of study drug. Both the value for the QTc and the decision to continue or stop the study drug will be recorded in the case report form. If the QTc in hospitalized patients cannot be assessed at 24-48 hours, study drug will be discontinued until the QTc can be assessed. If the daily on-study monitoring by study personnel for medication interactions indicates a potential interaction with a medication that treating clinicians feel is required for the optimal treatment of the patient and with which treating clinicians and the investigator feel it would be unsafe to administer hydroxychloroquine (including but not limited to: amiodarone; cimetidine; chloroquine; dofetilide; phenobarbital; phenytoin; sotalol), the study drug will be stopped and the reason will be recorded in the case report form.

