6.1 Baseline Variable Collection

- Presence or absence of inclusion and exclusion criteria
- Date and time of randomization
- Date of symptom onset
- Admission data: date and time of presentation, origin (home, skilled nursing facility, rehabilitation/LTACH, nursing home, outside hospital, outside ICU), location at enrollment (ED, hospital ward, ICU)
- Demographics (age, sex, race, ethnicity, height, weight)

- Comorbidities: AIDS, Leukemia, Malignant Lymphoma, Hemiplegia, Cerebrovascular Disease, A prior myocardial infarction, Congestive Heart Failure, Peripheral vascular disease, Dementia, COPD, Connective tissue disease, Peptic ulcer disease, History of hypertension, HIV positive (without AIDS), Alcoholism, Coronary artery disease, Rapidly fatal disease, Solid tumor, Liver disease, Diabetes mellitus, Moderate to severe kidney disease
- Acute signs and symptoms: altered mental status, acute hypoxemic respiratory failure, liver function tests, renal function, coagulation studies, chest imaging results
- Sequential Organ Failure Assessment (SOFA)³³ at enrollment
- Chronic use of medication: corticosteroids, ACE inhibitors, angiotensin receptor blockers, non-steroids anti-inflammatory drugs, other
- Receipt of open label antivirals between hospital presentation and enrollment: chloroquine, hydroxychloroquine, remdesivir, lopinavir/ritonavir, other
- Receipt of open label immunomodulators between hospital presentation and enrollment: corticosteroids, tocilizumab, sarilumab, interferon β , other
- Receipt of convalescent plasma between hospital presentation and enrollment
- Receipt of azithromycin between hospital presentation and enrollment
- Receipt of invasive mechanical ventilation, non-invasive ventilation, high-flow nasal cannula, vasopressors, and oxygen therapy at enrollment
- Highest fraction of inspired oxygen, lowest arterial oxygen saturation, highest respiratory rate, lowest systolic blood pressure, highest heart rate in the 12 hours prior to enrollment
- Diagnosis of Acute Respiratory Distress Syndrome (ARDS) by Berlin Criteria³³ at enrollment
- COVID Ordinal Outcomes Scale at enrollment

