9.1.1 Potential risks of receiving hydroxychloroquine

Potential risks of receiving hydroxychloroquine can be classified based on their severity as Major or Minor. Major potential risks of receiving hydroxychloroquine include:

- 1) Neurological System
 - a) Seizure – Hydroxychloroquine can lower the seizure threshold and co-administration of hydroxychloroquine with other medications known to lower the seizure threshold has been reported to increase the risk of seizures. This trial protocol excludes patients with a seizure disorder.
 - b) Psychosis – A small number of case reports describe psychosis in patients on long-term treatment with hydroxychloroquine,³⁹ but has not been described with short-term treatment.
 - c) Suicidal behavior - Suicidal behavior has been rarely reported in patients on long-term treatment with hydroxychloroquine for rheumatologic disorders,⁴⁰ but not with short-term therapy.
- 2) Circulatory system
 - a) Cardiac arrhythmias
 - i) Ventricular arrhythmias and torsades de pointes – Hydroxychloroquine can prolong the QT interval and ventricular arrhythmias and torsades de points have been reported in patients taking hydroxychloroquine. This trial protocol excludes patients with a prolonged QTc on baseline EKG and history of prolonged QTc syndromes, assesses the QTc after receipt of study drug, monitors daily for co-administration of medications that prolong the QTc and specifies criteria for stopping the study drug based on prolonged QTc.
 - ii) Cardiomyopathy, sick sinus syndrome, atrioventricular block, or bundle branch block – Cardiomyopathy and conduction system disease have rarely been reported among patients on long-term hydroxychloroquine,⁴¹ but have not been reported among patients receiving less than 3 months of therapy.
- 3) Digestive system
 - a) Liver injury – Fulminant hepatic failure has been reported in at least two cases from long-term administration of hydroxychloroquine.⁴² Porphyrria cutanea tarda appears to be a risk factor for liver injury from hydroxychloroquine. This trial protocol excludes patients with porphyria cutanea tarda.
 - b) Increased cyclosporine or digoxin levels – hydroxychloroquine can increase levels of cyclosporine or digoxin for patients being co-administered these medications. This trial protocol monitors daily for receipt of medications that interact with hydroxychloroquine and notifies treating clinicians about potential medication interactions.
- 4) Endocrine system

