14. APPENDICES

Appendix A. Schedule of Events

Study Activity	Pre-Enrollment	Day 1	Day 2	Day 3	Day 4	Day 5	Day 8	Day 15	Day 29	3 Months	6 Months	12 Months
Eligibility assessment	X											
EKG	X		X ^a									
Pregnancy test (if applicable)	X											
Informed consent	X											
Demographic and baseline variable collection		X										
Randomization		X										
Study drug delivery		X	X	X	X	X						
Assessment for study drug adherence		X	X ^a	X ^a	X ^a	X ^a	X ^b					
Safety monitoring for adverse events		X	X ^a	X ^a	X ^a	X ^a	X ^b	X ^b	X ^b			
Assessment of COVID ordinal outcome score	X		X ^a	X ^a	X ^a	X ^a	X ^b	X ^b	X ^b			
Mortality assessment								X ^b	X ^b			
28-day in-hospital outcomes (chart review)									X			
Long-term outcomes										X ^c	X ^c	X ^c

- a. Assessed only if patient remains hospitalized.
- b. Assessed by telephone follow-up if the patient has been discharged.
- c. Assessed in selected patients in-person, or by telephone or videophone.

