4.2 Exclusion Criteria

1. Prisoner
2. Pregnancy
3. Breast feeding
4. Unable to randomize within 10 days after onset of acute respiratory infection symptoms
5. Unable to randomize within 48 hours after hospital arrival
6. Seizure disorder
7. Porphyria cutanea tarda
8. QTc >500 ms on electrocardiogram within 72 hours prior to enrollment
9. Diagnosis of Long QT syndrome
10. Known allergy to hydroxychloroquine, chloroquine, or amodiaquine
11. Receipt in the 12 hours prior to enrollment, or planned administration during the 5-day study period that treating clinicians feel cannot be substituted for another medication, of any of the following: amiodarone; cimetidine; dofetilide; phenobarbital; phenytoin; sotalol
12. Receipt of >1 dose of hydroxychloroquine or chloroquine in the 10 days prior to enrollment
13. Inability to receive enteral medications
14. Refusal or inability to be contacted on Day 15 for clinical outcome assessment if discharged prior to Day 15
15. Previous enrollment in this trial
16. The treating clinical team does not believe equipoise exists regarding the use of hydroxychloroquine for the treatment of this patient

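### The numeric QTc from the eligibility EKG is not a listed baseline variable, so the SAP's only QTc analysis, an unadjusted display at 24-48 h in inpatients, has no baseline to set against it

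*SAP*

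**What the plan says.** **Before randomization.** The EKG row of the schedule of events (Protocol Appendix A) has a pre-enrollment mark with no footnote, so it applies to everyone. The reading serves exclusion 8: "QTc >500 ms on electrocardiogram within 72 hours prior to enrollment" (SAP 4.2; the same criterion is in Protocol 3.2). The risk section describes the same step: "This trial protocol excludes patients with a prolonged QTc on baseline EKG" (Protocol 9.1.1). What Protocol 6.1 lists for collection from eligibility is "Presence or absence of inclusion and exclusion criteria". No QTc value appears in 6.1, and 6.2 has no QTc item.

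**After randomization.** Protocol 4.5 calls for a QTc from an EKG or "rhythm strip performed 24-48 hours after administration of the first study medication". In Appendix A the Day 2 EKG carries the footnote "Assessed only if patient remains hospitalized", and 4.5 lets a patient discharged before the reading continue study drug without it. Protocol 4.6, in its paragraph on QTc assessed after randomization, says "Both the value for the QTc and the decision to continue or stop the study drug will be recorded in the case report form".

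**Analysis.** SAP 7.7 lists "QTc measurement on Study Day 2 (24-48-hour time window") among variables to be shown by arm at each time they are measured. It describes no baseline value, change or adjusted estimate. QTc is absent from the safety outcomes (SAP 6.3 and Appendix A) and from the on-study list (SAP Appendix C). No table is planned for post-randomization QTc >500 ms, the threshold used in Protocol 4.6.

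**The concern.** The protocol treats QT prolongation as a known risk of the drug and builds exclusions, on-study monitoring and a rule for interrupting study drug around it. The one numeric QTc comparison in the SAP is two post-dose distributions side by side.

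The other variables in SAP 7.7 have listed counterparts before randomization: the ordinal scale and SOFA score at enrollment, and the oxygenation data behind the S/F ratio. QTc is the exception, although its baseline tracing must exist for the exclusion to be applied. That looks like an omission rather than a choice.

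Three things are at stake. The arm difference is estimated less precisely than it need be. Change from baseline cannot be described from the listed data. And because the 24-48 h value is required only in patients still hospitalized, the comparison is made in a subset formed after randomization, with no listed means of checking whether that subset had similar QTc at baseline in the two arms.

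**Working it through.** The documents state no sample size, power or precision for QTc, so there is no planned figure to reproduce. The check is of the text, followed by the size of the consequence on assumed inputs.

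**Text, side by side**

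| Item | Eligibility EKG | 24-48 h reading |
|---|---|---|
| Who has it (Protocol Appendix A) | All patients | Those still hospitalized |
| Numeric value listed for recording | No (6.1, 6.2) | Yes (4.6) |
| In the SAP | Criterion only (4.2) | By-arm display (7.7) |

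**Inputs**
- From the documents: 510 patients randomized 1:1, so 510/2 = 255 per arm.
- Assumed, because the documents give none: QTc SD 25 to 35 ms (30 for illustration), baseline-to-follow-up correlation rho 0.3 to 0.8, and 60% to 100% of patients with a 24-48 h value (0.6 x 255 = 153 per arm at the low end).

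**Formulas**
- Follow-up value only: SE = SD x sqrt(2/n), with 95% half-width 1.96 x SE.
- Adjusted for baseline (ANCOVA): variance multiplied by 1 - rho^2.
- Plain change score: variance multiplied by 2(1 - rho).

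**Follow-up value only, SD 30 ms, 255 per arm:** SE = 30 x sqrt(2/255) = 2.66 ms and half-width 5.2 ms. Power for an illustrative 5 ms difference at two-sided 0.05 is 47%.

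**With baseline, same SD and n:**

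| rho | Adjusted variance factor | Cut in variance | Equivalent multiple of patients | Half-width (ms) | Power for 5 ms | Change-score factor |
|---|---|---|---|---|---|---|
| 0.3 | 0.91 | 9% | 1.1 | 5.0 | 51% | 1.40 |
| 0.5 | 0.75 | 25% | 1.3 | 4.5 | 58% | 1.00 |
| 0.7 | 0.51 | 49% | 2.0 | 3.7 | 75% | 0.60 |
| 0.8 | 0.36 | 64% | 2.8 | 3.1 | 88% | 0.40 |

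Over SD 25 to 35 ms and 60% to 100% measured, the unadjusted half-width runs from 4.3 to 7.8 ms. Adjusted at rho 0.7, it runs from 3.1 to 5.6 ms.

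**Chance difference in mean baseline QTc (95% range, SD 30 ms):** about +/-5.2 ms with 255 per arm and +/-6.7 ms with 153 per arm. From the listed data, a difference of this size would go unseen.

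**Change score.** It has lower variance than the follow-up value alone only when rho exceeds 0.5, and at every rho in the table its factor is larger than that of the adjusted estimate. Baseline therefore belongs in the model as a covariate.

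**The case against.** The strongest reply is that QTc is not an outcome of this trial. It is a monitoring measurement displayed descriptively, and the listed outcomes closest to QT risk (atrial arrhythmia, ventricular arrhythmia, cardiac arrest) are analyzed by arm through Study Day 29, including after discharge. That stands. A reader might infer that the trial has no usable QT safety comparison; the documents do not support that.

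A reader might also infer that a drug effect could not be told apart from a chance baseline imbalance. That goes too far. If all patients were measured, randomization would keep a comparison of follow-up values unbiased, and its confidence interval would already allow for chance imbalance. The inpatient-only requirement weakens this somewhat, but discharge before a 24-48 h reading is the only selection the plan describes, and nothing in the documents shows that it differs by arm under blinding. Balance of the measured subset can also be examined on age, sex, comorbidities, SOFA, ordinal score and medications, though not on QTc itself.

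Nor do the documents show that the eligibility value is lost. Protocol 3.5 describes an electronic eligibility form that is not reproduced, SAP 7.7 does not present its list as exhaustive, the SAP has no baseline-characteristics section for any variable, and the tracing should be in the chart. What stands is that the value is not listed and no analysis uses it.

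QTc readings above 500 ms are partly visible through the reasons for missed doses (SAP Appendix C) and adverse event reporting, but neither gives a count over the number assessed.

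Finally, every size input is assumed. The eligibility EKG may be up to 72 h before enrollment and the later reading may be a rhythm strip, and both could lower the correlation. At rho 0.3 the half-width falls only from 5.2 to 5.0 ms.

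**Conclusion.** The point holds as a gap in listed data and planned analysis. A pre-enrollment EKG is scheduled for everyone and used for exclusion, yet its numeric QTc is not a listed baseline variable, and the SAP's sole QTc analysis is an unadjusted by-arm display required only in inpatients.

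The cost is mainly precision, description of change, and the check on whether the measured subset started with similar QTc. With correlation assumed between 0.3 and 0.8, adjustment would cut the variance of the QTc difference by 9% to 64%. The millisecond figures also rest on an assumed SD and an assumed share measured.

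It is not a demonstrated bias. The primary analysis, the stopping boundaries, and the arrhythmia and cardiac arrest outcomes are untouched. It is worth correcting because the remedy is cheap and clearly better than the stated display.

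**What to change.** **Protocol 6.1:** list the QTc value (ms) from the eligibility EKG, with its date and time. If the case report form did not capture it, abstract it from the existing tracing.

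**SAP 7.7:**
- Show baseline QTc by arm for the patients who have a 24-48 h value.
- Estimate the 24-48 h arm difference, with a 95% confidence interval, from a regression with baseline QTc as a covariate, not from a plain change score.
- Report by arm the number assessed and the n (%) with any post-randomization QTc >500 ms.

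Adjustment addresses selection only so far as it runs through baseline QTc, so the number assessed in each arm should appear beside the estimate.

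**Cost:** a small amount of data abstraction, one regression and one extra table row. It needs no new EKG and changes no clinical rule.
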